3.2 Schedule of Visits and Assessments

The schedule of procedures is provided in **Appendix A**. The screening period will be up to 4 weeks. On the day of first study drug administration (Day 1), eligible subjects will be randomized to a 12-week, double-masked treatment period (a total of 4 doses given at approximately monthly intervals). Subjects will visit the study clinic on Day 1 and Weeks 4, 8, and 12 during the Treatment Phase. The visit window for these visits is -3 days to +7 days. All subjects will visit the clinic at Weeks 16, 20, and 24 after the last study drug administration or sham procedure for safety and ophthalmic assessments. The visit window for Weeks 16, 20, and 24 is ±7 days. For ED visits, the visits will be windowed according to the Protocol windows defined above and in **Table 1**.

Summaries and analyses utilizing timepoints will be completed using the nominal visit recorded in the electronic case report form (eCRF), except in the case of ED visits where the visit will be windowed to a scheduled visit using **Table 1**. In the case where a subject has a scheduled visit and a windowed ED

visit mapped to the same visit name, the observation closest to the planned study day will be used for analysis.

Table 1. Study Visit Windows for Early Discontinuation Visits

Scheduled Visit	Planned Study Day	Visit Window
Day 1	1	N/A
Week 4	28	15-42
Week 8	56	43-70
Week 12	84	71-98
Week 16	112	99-126
Week 20	140	127-154
Week 24	168	155-182

4. Study Treatments

Subjects will be randomized by the Interactive Response Technology (IRT) in a 1:1:1 ratio to 1 of the 3 treatment groups: KVD001 Injection (6 µg/eye or 3 µg/eye) or sham. Allocation to the treatments will be stratified by baseline BCVA (≤ 55 letters vs > 55 letters) and CST at Screening (≤ 450 µm vs > 450 µm) as determined by the study center.

1:1:1 randomization:

- KVD001 6 µg by IVT injection;
- KVD001 3 µg by IVT injection;
- Sham procedure.

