4.2 Masking and Unmasking

This is a double-masked study. Subjects, Investigators and site staff, the sponsor [REDACTED] [REDACTED] staff are masked to the treatment group assignments during the randomization process and for the duration of the study.

Under normal circumstances, the mask should not be broken. When medically necessary, an Investigator may need to determine what treatment has been assigned to a subject. The Investigator will contact the Sponsor with the details of the emergency unmasking request. The sponsor will make the final determination if the unmasking request will be granted. If granted, the unmasking information may be accessed through the use of an IRT system or provided by the unmasked designee. The Investigator must also indicate in source documents and in the eCRF that the mask was broken and provide the date, time, and reason for breaking the mask.

5. Sample Size and Power Considerations

The proposed sample size (41 per treatment group) will provide approximately 80% power to detect a difference in change from baseline of 5 letters between either of the KVD001 treatment groups and sham based on a two-sided, two-sample t-test with significance level 0.05 and assuming a pooled standard deviation (SD) of 7.5 letters.

6. Data Preparation

Data management procedures, including database design, selection of the data dictionary, and coding of all AEs and medications, will be performed [REDACTED]. All reported study data will be recorded on [REDACTED] eCRFs supplied [REDACTED]. Clinical personnel at the study center and [REDACTED] are responsible for ensuring that the protocol is followed and that the eCRFs are properly completed.

After data are entered into the clinical study database, electronic edit checks will be performed, including checks for missing data, out of range values, discrepancies within and across visits, and cross checks between different data tables. All data validation specifications and procedures are detailed in the Data Validation Manual (DVM), and manual data checks are documented in the Study Report Specifications (SRS). When the database has been declared to be complete and accurate, the database will be locked and treatment codes unmasked. Any changes to the database after that time can only be made with the approval of the Sponsor in consultation with Ora, Inc. [REDACTED]

All final analyses outlined in this document will be performed after:

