7.3 Safety Set

[figure not shown]
The Safety Set (SAF) will include all randomized subjects who received at least one dose of study treatment. Subjects will be included in the analysis according to the treatment received.

8. General Statistical Considerations

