13.3 Secondary Analyses

The secondary endpoints are the following:

- Change from baseline in CST as measured by SD-OCT
- Proportion of eyes with a ≥ 2 step improvement from baseline in DRSS score
- Change from baseline in BCVA letter count as measured by ETDRS
- Proportion of SEs with ≥ 5 , ≥ 10 , and ≥ 15 BCVA letter gain from baseline and the proportion of SEs with ≥ 5 , ≥ 10 , and ≥ 15 BCVA letter loss from baseline.

Change from baseline in BCVA letter count as measured by ETDRS in the study eye and change from baseline in CST in the study eye as measured by the central image reading center (CIRC) using SD-OCT will be analyzed using the same method described for the primary efficacy analysis. Note that change from baseline in CST will be in favor of KVD001 if the treatment difference is < 0 .

The difference in proportion of SEs with improvement of 2 or more steps on the ETDRS DRSS score between each KVD001 injection dose and the sham and between the KVD001 Injection doses will be summarized by visit using discrete summary statistics, including 95% Clopper-Pearson CIs for each treatment group. The difference in proportions between each KVD001 Injection dose and the sham and between the KVD001 Injection doses will be analyzed using a Pearson's chi-squared test. 95% Clopper-

Pearson CIs for the differences in proportions will also be calculated. Fisher's exact tests and exact CIs will be employed in cases of expected counts <5.

The proportion of SEs with ≥ 5 , ≥ 10 and ≥ 15 BCVA letter change (gain and loss) between baseline and each post-baseline visit will be analyzed using the same method described for the proportion of SEs with improvement of 2 or more steps on the ETDRS DRSS score. Additionally, as an exploratory endpoint, the proportion of SEs with any BCVA letter loss between baseline and each post-baseline visit will be summarized similarly. Note that the categorizations of ≥ 5 , ≥ 10 and ≥ 15 BCVA letter change (gain and loss) or any BCVA letter loss are not mutually exclusive.

14. Safety Analyses

All safety data analyses will be performed on the safety population and displayed in subject data listings and summarized in tables. No statistical inferential testing will be performed for safety variables.

Safety endpoints include AEs, manifest refraction/BCVA, slip lamp biomicroscopy, dilated ophthalmoscopy, intraocular pressure (IOP), SD-OCT, EDTRS DRSS, physical exam findings, laboratory test results, and vital signs.

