- Number of subjects with TEAEs leading to death; and
- Number of subjects with TEAEs by maximum severity.

Overall summaries of AEs will be presented for the following classes of events:

- All AEs (ocular & non-ocular)
- Ocular events for each eye (study eye and fellow eye)
- Non-Ocular events

Frequencies and percentages of subjects with TEAEs, serious TEAEs, TEAEs leading to study drug discontinuation, and treatment-related TEAEs will be provided by treatment group by SOC and PT.

Furthermore, summaries will be given of subjects with TEAEs:

- by SOC, PT, and maximum severity;
- by SOC, PT, and strongest relationship;
- by SOC and PT for SAEs;
- by SOC and PT for TEAEs related to study drug; and
- by SOC, PT, and time of onset (i.e., Day 1 to Week 4 [Days 1-28], > Week 4 to Week 8 [Days 29-56], > Week 8 to Week 12 [Days 57-84], > Week 12 to Week 16 [Days 85-112], > Week 16 [> Day 112]).

Separate analyses will be performed for ocular specific AEs, and all AEs (including systemic).

Summaries of preferred terms (without regard to SOC) will be presented for TEAEs and the most frequent TEAEs (occurring in $\geq 5\%$ of patients treated with KVD001 6 μg or KVD001 3 μg).

Post-treatment AEs, defined as AEs that started or worsened more than 28 days after last injection, will also be summarized.

Subject listings of all AEs including verbatim text will be provided as well as listings of deaths, SAEs, and AEs causing premature discontinuation of study drug.

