14.3.1.2.2	Ocular Treatment-Emergent Adverse Events by Eye, System Organ Class, and Preferred Term	SAF Population
14.3.1.2.3	Serious Adverse Events by System Organ Class and Preferred Term	SAF Population
14.3.1.2.4	Ocular Serious Adverse Events by Eye, System Organ Class, and Preferred Term	SAF Population

[figure not shown]
14.3.1.2.5	Treatment-Emergent Adverse Events Leading to Study Drug Discontinuation by System Organ Class and Preferred Term	SAF Population
14.3.1.2.6	Ocular Treatment-Emergent Adverse Events Leading to Study Drug Discontinuation by Eye, System Organ Class, and Preferred Term	SAF Population
14.3.1.2.7	Treatment-Related Treatment-Emergent Adverse Events by System Organ Class and Preferred Term	SAF Population
14.3.1.2.8	Ocular Treatment-Related Treatment-Emergent Adverse Events by Eye, System Organ Class, and Preferred Term	SAF Population
14.3.1.2.9	Post-Treatment Adverse Events by System Organ Class and Preferred Term	SAF Population
14.3.1.3.1	Treatment-Emergent Adverse Events by System Organ Class, Preferred Term, and Maximum Severity	SAF Population
14.3.1.3.2	Ocular Treatment-Emergent Adverse Events by Eye, System Organ Class, Preferred Term, and Maximum Severity	SAF Population
14.3.1.4.1	Treatment-Emergent Adverse Events by System Organ Class, Preferred Term, and Relationship to Study Drug	SAF Population
14.3.1.4.2	Ocular Treatment-Emergent Adverse Events by Eye, System Organ Class, Preferred Term, and Relationship to Study Drug	SAF Population
14.3.1.5.1	Treatment-Emergent Adverse Events by System Organ Class, Preferred Term, and Time of Onset	SAF Population
14.3.1.5.2	Ocular Treatment-Emergent Adverse Events by Eye, System Organ Class, Preferred Term, and Time of Onset	SAF Population
14.3.1.6.1	Treatment-Emergent Adverse Events by Preferred Term	SAF Population
14.3.1.6.2	Ocular Treatment-Emergent Adverse Events by Eye and Preferred Term	SAF Population
14.3.1.7.1	Most Frequent ($\geq 5\%$ of KVD001-Treated Subjects) Treatment-Emergent Adverse Events by Preferred Term	SAF Population
14.3.1.7.2	Most Frequent ($\geq 5\%$ of KVD001-Treated Subjects) Ocular Treatment-Emergent Adverse Events by Eye and Preferred Term	SAF Population
14.3.4.1	Best Corrected Visual Acuity (Letter Count) by Visit and Eye	SAF Population
14.3.4.2	Central Subfield Thickness (μm) by Visit and Eye	SAF Population
14.3.4.3	Early Treatment Diabetic Retinopathy Study Diabetic Retinopathy Severity Score in the Study Eye by Visit	SAF Population

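### SAP 14.1 selects the most frequent TEAEs on KVD001 rates alone, so two descriptive tables tilt against KVD001 for low-rate terms; separately, the text and the table titles do not settle which 5% rule applies

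*SAP*

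**What the plan says.** SAP 14.1 plans preferred-term summaries of all TEAEs and of a shorter, more frequent subset: "Summaries of preferred terms (without regard to SOC) will be presented for TEAEs and the most frequent TEAEs (occurring in". The threshold that follows is 5% or more "of patients treated with KVD001 6" µg or with KVD001 3 µg. Sham is not named.

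SAP Section 19 gives the matching tables, 14.3.1.7.1 (all TEAEs) and 14.3.1.7.2 (ocular, by eye). Their titles put the threshold at 5% or more "of KVD001-Treated Subjects) Treatment-Emergent Adverse Events by Preferred Term" (wording of 14.3.1.7.1; the ocular title follows the same pattern). Again sham is absent, and the two doses are not named separately.

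Three other provisions bear on the point:

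- SAP 14.1 also plans TEAE frequencies without any cut-off, which "will be provided by treatment group by SOC and PT". SAP Section 19 lists unfiltered tables by SOC and preferred term (14.3.1.2.1, 14.3.1.2.2) and by preferred term alone (14.3.1.6.1, 14.3.1.6.2).
- SAP Section 14 states: "No statistical inferential testing will be performed for safety variables".
- Protocol 8.6.1 asks for a summary of the most frequent AEs but gives no threshold and restricts it to no arm. The KVD001-only filter therefore comes from the SAP.

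**The concern.** If a term enters a table because its KVD001 count is high, and KVD001 is then compared with sham in that same table, chance highs on KVD001 are kept and chance highs on sham are not. The listed terms then lean towards a KVD001 excess even when the arms do not differ. Terms that are frequent on sham and rare on KVD001 tend not to appear.

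No test accompanies these tables, so they will be read by eye, and a short table of frequent events is easily taken as the by-arm safety picture.

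A second and separate matter is that the text points to either dose while the titles can be read as both doses pooled. Two programmers could produce different lists from the same data.

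**Working it through.** **Inputs**

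- Arm size: "The proposed sample size (41 per treatment group) will provide approximately 80% power to detect a difference in change from baseline of 5 letters" (SAP Section 5), with "1:1:1 randomization" (SAP Section 4). That is 41 on each dose, 82 on KVD001 and 41 on sham.
- Analysis set: "The Safety Set (SAF) will include all randomized subjects who received at least one dose of study treatment" (SAP 7.3). I assume that all 41 per arm are treated.
- True TEAE rates: none in the documents. Assumed equal in all three arms, p from 1% to 20%.
- Display: I assume that the tables show a sham column beside the two doses.

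The plan states no figure on this point, so there is none to reproduce.

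**Step 1: cut-offs**

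- Either dose: 0.05 × 41 = 2.05, so 3 subjects on one dose (3/41 = 7.3%; 2/41 = 4.9% fails).
- Pooled: 0.05 × 82 = 4.1, so 5 subjects on KVD001 (5/82 = 6.1%).

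Any pooled count of 5 or more has at least 3 on one dose, so the pooled list is a subset of the either-dose list. The rules differ for splits of 3+0, 3+1 and 4+0. The chance that a term enters under the either-dose rule only is 7.0% at p = 2%, 13.3% at 3%, 17.0% at 5% and 3.4% at 10%.

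**Step 2: expected difference among listed terms when the arms are equal**

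Let X ~ Binomial(41, p), q = P(X ≤ 2) and m = P(X=1) + 2·P(X=2). Sham is independent of the selection, so its mean among listed terms stays at p.

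- Either dose: mean KVD001 rate = (82p − 2mq) / [82(1 − q²)].
- Pooled: mean KVD001 rate = E[Y | Y ≥ 5]/82, with Y ~ Binomial(82, p).

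At p = 3%, q = 0.8756 and m = 0.3637 + 2 × 0.2250 = 0.8137. The either-dose rate is (2.46 − 2 × 0.8137 × 0.8756) / [82 × (1 − 0.8756²)] = 1.035/19.13 = 5.4%, against 3.0% on sham. The pooled rule gives 6.7% against 3.0%.

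Exact enumeration of the three counts gives:

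| True rate, all arms | Mean excess, either dose (points) | Mean excess, pooled (points) | P(KVD001 above sham, if listed): either / pooled |
|---|---|---|---|
| 2% | +2.85 | +4.48 | 0.84 / 0.95 |
| 3% | +2.41 | +3.74 | 0.75 / 0.89 |
| 5% | +1.56 | +2.43 | 0.62 / 0.73 |
| 7% | +0.88 | +1.42 | 0.54 / 0.60 |
| 10% | +0.28 | +0.49 | 0.49 / 0.50 |
| 15% | +0.02 | +0.04 | 0.47 / 0.48 |
| 20% | 0.00 | 0.00 | 0.48 / 0.48 |

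For scale, one subject in 41 is 2.4 points. At 3% a given term is listed with probability 1 − 0.8756² = 23% (either dose) or 10% (pooled). In an unfiltered table the expected difference is 0.

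**Step 3: terms frequent only on sham**

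Assume 15% on sham and 3% on each dose. The term is omitted with probability q² = 0.8756² = 0.77 (either dose), or P(Binomial(82, 0.03) ≤ 4) = 0.90 (pooled). With 10% on sham and 2% on each dose, the figures are 0.905 and 0.975.

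**Step 4: a rule that treats the arms alike**

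If a term enters when any of the three arms reaches 5%, the expected rates among listed terms are equal by symmetry. At p = 3% they are 4.5% on KVD001 and 4.5% on sham, and the difference is 0 at every p. Selection still raises the level (4.5% for a true 3%), but equally in each arm.

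**The case against.** The case for leaving the tables alone has real weight.

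- **The effect is confined to low-rate terms.** A reader might infer that these tables show a KVD001 excess throughout. They do not. The excess is an average, it fades as the true rate rises, and at 10% a listed term is about as likely as not to show KVD001 above sham. The rates themselves are assumptions. This stands, and it limits the claim to terms near or below the cut-off.
- **The title may be only a short label.** SAP 14.1 names the doses separately, and the visible SAP defines no combined KVD001 group, so the title can be read as the text rule. A reader might infer two conflicting rules, or that the mismatch causes the excess. The documents support neither. The wording is unreconciled, and the excess comes from one-sided selection under either reading. The pooled figures apply only if the titles are taken that way.
- **Nothing is lost from the report.** A reader might infer that sham-excess events, such as worsening macular edema, are hidden. They are not. Tables 14.3.1.6.1 and 14.3.1.6.2 list every term. Letter loss (SAP 13.3, 14.2), CST (14.3), DRSS worsening (14.4), and rescue and discontinuation for rescue (Section 9) are all reported by arm. This stands in full.
- **No decision turns on it.** No safety test is run, and the tilt makes KVD001 look worse, not better. A table of what happens on the drug is a legitimate presentation choice. This keeps the point minor. It does not make the by-arm comparison in these two tables even-handed, and it does not settle which rule the programmer should apply.

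**Conclusion.** The point holds as a small presentation flaw in Tables 14.3.1.7.1 and 14.3.1.7.2. Selecting on KVD001 alone gives an expected KVD001 excess under no true difference of roughly one subject in 41 for terms with true rates of 2% to 5% (somewhat more if the rule is pooled). For common terms it is negligible. Terms frequent only on sham will usually be missing from these two tables, though not from the report.

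The ambiguity between text and titles is a separate matter. It changes which terms are listed and the size of the tilt, but does not cause it.

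The figures rest on 41 treated per arm, independent counts, a displayed sham column, and assumed rates: equal in all arms for the excess, and as stated for the omission probabilities. No efficacy result, safety test or stored safety data is affected.

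**What to change.** Use one rule in SAP 14.1 and in the titles of Tables 14.3.1.7.1 and 14.3.1.7.2: preferred terms occurring in at least 5% of subjects in any treatment group (6 µg, 3 µg or sham), with all three arms shown. This removes the expected difference under equal rates, settles the either-dose or pooled question, and brings in terms frequent only on sham. In the 15% versus 3% example the omission probability falls from 0.77 to 0.8756² × 0.0431 = 0.03, where 0.0431 is the chance of 2 or fewer of 41 at 15%.

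The cost is a wording change and one filter condition, with no new data. The tables become a few rows longer: at an equal 3% rate, the chance that a term is listed rises from 23% to 1 − 0.8756³ = 33%.

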14.2 BCVA ETDRS

The BCVA of both eyes (study eye and fellow eye) will be assessed using the ETDRS protocol at the beginning of every study visit and will be summarized at each visit using quantitative summary statistics for each eye by treatment group.

BCVA of both eyes will be measured consistent with the standard procedure developed for the ETDRS. The number of letters read correctly will be counted and the total BCVA letter score will be reported. The total BCVA letter score will be summarized for each treatment group and over all subjects using continuous descriptive statistics at each visit for each eye (study eye and fellow eye). Change from baseline will also be summarized by treatment group and visit for ██████ eye (study eye and fellow eye).

The number of subjects (by eye [study eye and fellow eye]) with a gain or loss in BCVA letter score ≥ 15 , ≥ 10 , and ≥ 5 or any BCVA letter loss from baseline will be summarized using counts and percentages for each treatment group and over all subjects at each visit.

[figure not shown]
A subject listing of BCVA and manifest refraction will also be produced.

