3.1 General Study Design

This is a phase 2a, randomized, double-masked, sham-controlled, 3-arm study to evaluate the efficacy, safety, and tolerability of KVD001 Injection as monotherapy in adult subjects with ciDME who have had prior anti-VEGF treatment. Approximately 123 eligible subjects will be randomized into the study.

Subjects will undergo screening for fulfilling the inclusion and exclusion criteria in order to be eligible for this study. Eligible subjects will be stratified based on visual acuity and CST, and then randomly

assigned in a 1:1:1 ratio into the 3 groups described below. Stratified randomization will be performed centrally by visual acuity and CST at Day 1.

- KVD001 6 µg by IVT injection;
- KVD001 3 µg by IVT injection;
- Sham procedure.

Rescue intervention (e.g., anti-VEGF, focal/grid macular laser photocoagulation, IVT steroids) may be administered due to worsening DME (i.e., attributable to worsening DME and not another cause) if either of the following occurs and, where possible, after consultation with the Medical Monitor:

- During Treatment Phase
 - BCVA deteriorates 3 lines (15 letters) or more from baseline
 - CST worsening of >100 µm from baseline
- During Follow up Phase (i.e., after week 16)
 - BCVA deteriorates 3 lines (15 letters) or more from highest BCVA during treatment phase or baseline
 - CST worsening of >100 µm from lowest CST during treatment phase or baseline.

Subjects who receive a rescue intervention in the study eye will be discontinued from further study participation. The Week 24/Early Discontinuation (ED) evaluations should be collected prior to study discontinuation and prior to administration of the rescue medication. Details regarding the medications used as rescue treatment must be entered as concomitant medications for the respective study subject.

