8.2 Missing Data Conventions

Partial/missing start and end dates for AEs and concomitant medications will be imputed to create complete dates for the determination of treatment-emergent AEs or medications concomitant with study treatment.

Partial/missing start dates:

- Dates with missing day only will be imputed as the 1st of the month unless the month and year are same as the month and year of first dose of study medication, in which case missing day will be imputed as the first dose day of study medication.
- Dates with both day and month missing will be imputed as 1 Jan unless the year is same as the year of first dose of study medication, in which case missing day and month will be imputed as the first dose day and month of study medication.
- Completely missing dates will be imputed as the first dose date of study medication unless the end date is on or before the first dose date of study medication, in which case missing date will be imputed as 1 Jan of the same year as the end date.

Partial/missing end date:

- Dates with missing day only will be imputed as the last day of the month unless the month and year are the same as the month and year of the last dose of study medication, in which case missing day will be imputed as the last dose day of study medication.
- Dates with both day and month missing will be imputed as 31 Dec unless the year is same as the year of the last dose of study medication, in which case missing day and month will be imputed as the last dose day and month of study medication.
- If the ongoing flag is missing or “Yes” then the date will not be imputed unless death date is available, in which case the missing date will be imputed as the death date.
- If the imputed date is after the date of death, then the end date will be set equal to the date of death.

The original dates will be displayed in data listings and the imputed dates will be used in derivations only (study day, treatment-emergence status, etc.).

The primary and secondary efficacy data analyses will be performed on the FAS [REDACTED]. An analysis using observed data only will also be performed in both the FAS and PPS. [REDACTED] will be used to impute missing data in the FAS for the analysis of the primary and secondary continuous efficacy variables. No exploratory efficacy endpoints or safety endpoints will be imputed.

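### No planned safety table counts the eyes that ever lost 15 or more letters, and the visit-by-visit rows cannot supply that number

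*SAP*

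**What the plan says.** SAP 14.2 counts, for the study eye and the fellow eye, gains and losses of at least 15, 10 and 5 letters and any loss. These "will be summarized using counts and percentages for each treatment group and over all subjects at each visit". The matching shell in SAP 19, Table 14.3.4.1, is titled "Best Corrected Visual Acuity (Letter Count) by Visit and Eye". Protocol 8.6.8 has the same visit-wise layout. On missing data, SAP 8.2 states: "No exploratory efficacy endpoints or safety endpoints will be imputed".

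SAP 3.1 sets the rescue rule. One treatment-phase criterion is "BCVA deteriorates 3 lines (15 letters) or more from baseline"; the other is a CST increase of more than 100 µm. Rescue "may be administered due to worsening DME (i.e., attributable to worsening DME and not another cause"). Its consequence is fixed: "Subjects who receive a rescue intervention in the study eye will be discontinued from further study participation". A final assessment at early discontinuation (ED) is planned before the subject leaves; on its timing, the same section says that these "evaluations should be collected prior to study discontinuation and prior to administration of the rescue medication".

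SAP 3.2 analyses data by nominal visit, "except in the case of ED visits where the visit will be windowed to a scheduled visit" using its Table 1. If a scheduled visit and an ED visit fall on the same visit name, only the value nearer the planned day is analysed.

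**The concern.** For a drug injected into the eye, the number of eyes that at any time lost 15 letters is a basic local safety result. Visit rows answer a different question: how many of the eyes measured at this visit are down 15 letters now. The two differ when some affected eyes leave after one appearance while others stay and are counted again. Here a 15-letter loss can itself lead to departure, so both patterns can occur in one arm.

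At stake is the reading of the late visits. If one arm has more rescues for visual loss, its Week 20 and Week 24 rows rest on the eyes that remain, and it may look no worse, or better, than an arm that kept its affected eyes. Safety is descriptive only (SAP 14), so these tables carry much of the evidence on vision.

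**Working it through.** The plan states no rate of 15-letter loss, so there is no figure to reproduce. The check is what the visit rows can and cannot determine.

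**Inputs.** 41 subjects per arm (SAP 5). Six post-baseline visits: Weeks 4, 8, 12, 16, 20 and 24. ED windows from SAP Table 1. The number of affected eyes per visit is an assumption.

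**1. Bounds from the rows.** Let c1 to c6 be the counts in the six rows and E the number of eyes that ever lost 15 letters and reached a row. Then max(c) ≤ E ≤ sum(c). With one eye in every row, 1 ≤ E ≤ 6, so E/41 runs from 1/41 = 2.4% to 6/41 = 14.6%.

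| Pattern (no other exits) | Week 4 row | Week 24 row | Ever lost |
|---|---|---|---|
| One eye affected at all six visits, stays | 1/41 = 2.4% | 1/41 = 2.4% | 1/41 = 2.4% |
| A different eye at each visit, each then leaves | 1/41 = 2.4% | 1/36 = 2.8% | 6/41 = 14.6% |
| Two different eyes at each visit, each then leaves | 2/41 = 4.9% | 2/31 = 6.5% | 12/41 = 29.3% |

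The first two patterns have identical counts in every row. Their percentages differ only through the denominator, taken here as subjects observed at the visit. That is inferred from the no-imputation rule; SAP 14.2 gives no denominator. A falling denominator does not settle the matter, because CST rescues and ordinary withdrawals lower it too.

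**2. Losses that reach no row.** Table 1 gives Week 8 (planned day 56) the window 43–70. Where both values fall in that window, the nearer to day 56 is kept.

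- Week 8 visit on day 56 (distance 0): an ED value on days 57–70 (distance 1 to 14) is dropped.
- Week 8 visit on day 53 (distance 3): ED values on days 60–70 are dropped; day 59 ties, and the SAP has no tie rule.
- Week 8 visit on day 63 (distance 7): ED values on days 64–70 (distance 8 to 14) are dropped.
- The Week 4 window opens on day 15, so an ED value on days 2–14 falls in no post-baseline row.

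A subject seen on day 56 without the loss, who returns on day 65 down 15 letters, has the pre-rescue evaluation and leaves, is therefore counted nowhere in the table. Such eyes add to the ever-lost number on top of E.

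**3. Direction of the late-visit error.** Take the second pattern. The Week 24 row reads 1/36 = 2.8%. If the five eyes that left would still have been down 15 letters, the figure without exits would be 6/41 = 14.6%. If all five would have recovered, it would be 1/41 = 2.4%. The row may understate loss, but the direction depends on what those eyes would have done.

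**4. Other outputs.**

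- Disposition (SAP 9) gives, by arm, subjects rescued before Week 16 and discontinuations for rescue medication, without the criterion met.
- AE tables have no letter threshold. Treatment-emergent events stop 28 days after the last injection (SAP 14.1); later ones go to Table 14.3.1.2.9, which has no by-eye version listed.
- Efficacy Tables 14.2.1.5.1 and 14.2.1.5.2 are also by visit. Their data-handling labels are blacked out, and nothing is assumed about them.
- Listing 16.2.8.1.1 holds every BCVA value, so the data exist but the count is not tabulated.
- By contrast, SAP 14.8 summarises maximum and minimum post-baseline vital signs, and SAP 14.10 gives shifts to post-baseline high and low for laboratory values.

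**The case against.** The best case against has four parts.

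First, a reader might infer that the rescue rule takes out every eye that loses 15 letters. The documents do not say so. Rescue is optional, is limited to worsening DME, and ends participation only when actually given in the study eye. A loss from another cause, including one due to the injection, does not meet the rule, and fellow eyes are untouched by it. This stands. It narrows the mechanism, but the rows fail to identify the ever-lost count even without rescue, because eyes can recur.

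Second, the failing value is normally counted once. If the loss is found at a scheduled visit, that row shows it; if at an ED visit, windowing usually places it. This also stands. The dropped value matters when the loss is first measured between visits.

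Third, unequal rescue is visible by arm in disposition, and the protocol requires clinically relevant deterioration to be recorded as an AE (6.2.1), with a broad visual-threat note under serious events (6.2.1.4). AE tables are subject-level counts of events at any time in their period. These outputs reduce the risk of a misleading late-visit comparison, but none gives the number of eyes at or beyond 15 letters.

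Fourth, this is an exploratory Phase 2a trial without inferential safety tests, and the count can be made by hand from listings. That limits the weight of the point; it does not argue against a nearly free row.

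**Conclusion.** The point holds as a gap in tabulation, not in data collection, and it does not touch the primary analysis. The planned safety tables do not give the number of eyes that ever lost 15 or more letters. With one eye per row and 41 per arm, the same counts fit 2.4% to 14.6% ever affected, before adding any loss dropped by the nearest-day rule. The range rests on the assumed one eye per row; the documents give no rate.

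Three stronger readings are not supported.

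- Late rows are biased low. That requires rescued eyes to have stayed down 15 letters; late rows may understate loss, and by different amounts per arm if rescue rates differ.
- A constant-risk model measures what is hidden. At an assumed 3% per visit, 1 − 0.97^6 = 16.7%, or 6.8 of 41. But that model makes every affected eye leave at once, so the visit counts add up to the ever-lost count, and both the rate and universal rescue are assumptions.
- The same argument covers IOP of 30 mmHg or more. IOP is not a rescue criterion, so the rescue mechanism does not apply.

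**What to change.** In SAP 14.2 and Table 14.3.4.1, add by eye and arm a row for loss of at least 5, 10 and 15 letters at any post-baseline assessment. Define this to include scheduled visits, ED values (also those not selected by the windowing rule or outside every window) and unscheduled measurements. Use all safety-set (SAF) subjects in the arm as denominator.

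For study eyes in that row, report how many were rescued, split by criterion met: BCVA, CST or both. State which CST reading is used, since Listing 16.2.8.2 carries both the reading centre's and the Investigator's. Keep the visit rows and state their denominator.

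The cost is one derived flag and a few table rows, using data already collected. No visit, assessment or clinical rule changes.
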